### 1. VERSION HISTORY

This is the first version.

### 2. INTRODUCTION

PF-07260437 is a T cell redirecting B7-H4 x CD3 bispecific mAb with 2 binding domains: a domain that recognizes tumor antigen B7-H4 with high affinity and a domain that recognizes CCI [REDACTED], expressed on T cells, with moderate affinity. Co-engagement of B7-H4 on tumor cells and CCI [REDACTED] on T cells leads to a tumor-localized T-cell cytotoxic response and reduces systemic CCI [REDACTED] targeting and toxicity. This mechanism circumvents the need for T cells to recognize specific antigenic peptides in the context of CCI [REDACTED] on malignant cells. Cytotoxicity is mediated by release and transfer of CCI [REDACTED] from the T cell to the B7-H4 expressing target cell. PF-07260437 addresses a significant unmet medical need for BrCa, as its target is expressed in the majority of BrCas across all molecular subtypes.

This statistical analysis plan (SAP) provides the detailed methodology for summary and statistical analyses of the data collected in Study PF-07260437. This document provides additional details for the planned analyses that are outlined in the protocol. This SAP was written in reference to the protocol dated June 23, 2021. Any major modifications of the endpoints or analyses will be reflected in further amendments to the protocol and SAP.

#### 2.1. Study Objectives, Endpoints and Estimands

##### 2.1.1 Primary Estimand(s)

###### Primary Estimand (DLT) for Part 1:

DLT rate estimated based on data from DLT-evaluable participants during the DLT-evaluation period (28 days for regimen without priming; 42 days for the regimen with priming (priming doses plus 2 full doses)) in Part 1.

Variable: Occurrence of DLTs.

Analysis population:

For the dose escalation without priming, DLT-evaluable participants defined as participants:

- who receive at least 1 dose of study treatment and experience DLT during the DLT-evaluation period (28 days),

OR

- who complete the DLT-evaluation period without DLT. Participants without DLTs who withdraw from study treatment before receiving at least 2 full doses of study drug for reasons other than treatment-related toxicity are not evaluable for DLT.

For the dose escalation with priming, DLT-evaluable participants defined as participants:

- who receive at least 1 dose of study treatment and experience DLT during the DLT-evaluation period (priming doses plus 2 full doses, eg, 42 days),

OR

- who complete the DLT-evaluation period without DLT. Participants without DLTs who withdraw from study treatment before receiving at least the priming dose and 2 full doses of study drug for reasons other than treatment-related toxicity are not evaluable for DLT.

Population-level summary measure: DLT rate defined as the number of DLT-evaluable participants with DLTs in the DLT-evaluation period divided by the number of DLT-evaluable participants in the DLT-evaluation period.

#### Primary Estimand for Parts 1 and 2:

Incidence of AEs estimated in the analysis population during the AE-evaluation period, defined as the time from the first dose to earliest of 28 days post last dosing date and day of new anti-cancer therapy-1 day.

Variable: Occurrence of AEs.

Analysis population: Safety analysis set defined as participants who receive at least 1 dose of study treatment without regard to tolerability or duration of treatment.

Population-level summary measure: Incidence of AEs defined as the number of participants with AEs in the AE-evaluation period divided by the number of participants in the analysis population. AEs will be summarized by type, frequency, severity (as graded by NCI CTCAE version 5), timing, seriousness, and relationship to treatment.

#### **2.2. Study Design**

This is an open label, multi-center, first-in-human Phase 1 dose escalation and dose expansion study to evaluate the safety, tolerability, PK, PD, and preliminary antitumor activity of PF-07260437, a B7-H4 x CD3 bispecific mAb in advanced or metastatic selected solid tumors (BrCa, OvCa and endometrial cancer). This study contains 2 parts, dose escalation (Part 1) and dose expansion (Part 2).

Part 1 contains dose escalation in participants with locally advanced or metastatic BrCa, OvCa or endometrial cancer that is resistant or intolerant to standard therapy or for whom no standard therapy is available, to determine the MTD and select the RDE. Participants with other advanced or metastatic high B7-H4 expressing tumors may be considered after discussion with and approval from sponsor.

Once the PF-07260437 monotherapy RDE is selected, either with or without priming, Part 2 dose expansion cohorts may be initiated to further evaluate the safety and preliminary antitumor activity of PF-07260437 monotherapy in advanced or metastatic 2L+ HR+ HER2- BrCa with high B7-H4 expression (Part 2A) and 2L+ TNBC with high B7-H4 expression (Part 2C) as well as unselected HR+ HER2- BrCa or TNBC (Part 2B).

### Part 1 Dose Escalation

Participants will receive escalating doses of PF-07260437 administered as SC injection with a starting dose level of 100 µg Q2W as monotherapy. Additional dosing frequency such as Q1W or Q3W may be considered if supported by emerging clinical PK, PD, and safety data. BLRM guided by EWOC principle will be used to guide the dose escalation process and determine the MTD/RDE. The maximum allowable PF-07260437 dose increment is 200% (dose tripling from the previous dose level) for cohorts but will be adjusted to no more than 100% (dose doubling from the previous dose level) following the observation of a DLT or if there are two Grade  $\geq 2$  clinically significant treatment-related AEs. For monotherapy without priming strategy, DLT will be assessed during the first 28 days. For monotherapy with priming, the DLT assessment period will extend to include priming doses plus 2 full doses (eg, first 42 days). Each dose level group will include approximately 3 participants, with at least 1 DLT evaluable participant per cohort in the first 2 cohorts and at least 2 DLT evaluable participants per dose level group in the remaining cohorts for Part 1. Per BLRM design, expanding additional participants at lower dose levels are allowed to assess safety. Dose escalation cohorts may be switched from SC administration to IV administration if SC administration is not considered as the preferred route due to severe skin toxicities, low PK exposure or other reasons. IV administration cohorts may initiate at a dose level that is no greater than 20% of the highest SC dose level that is deemed tolerable (eg, starting at 60 µg IV Q2W if 300 µg SC Q2W is deemed tolerable) depending on emerging PK and safety data.

A priming dose approach in the next dose level may be initiated if a dose level induces  $\geq$  Grade 2 CRS (lasting for  $>24$  hours) occurs in  $>1$  participant despite treatment with tocilizumab and/or vasopressors. If the dose escalation has reached the MTD and a priming dose has not been previously incorporated to the dose regimen, a priming dose escalation cohort to minimize  $C_{max}$  may be initiated based on clinical safety, PK/PD, and clinical efficacy.

The DLT period for SC or IV dosing without priming will be 28 days. The DLT period with priming will extend to include the duration of the priming doses and 2 full doses after priming (eg, if a priming dose is given on Day 1 and the first full dose on Day 15, the total DLT observation period will be 42 days). A traditional 2-parameter BLRM will be used to model the DLT relationship to the drug and inform dose escalation with or without priming. The maximum dose level increase will be 200% (dose tripling from the previous dose level).

### Part 2 Dose Expansion

The Part 2 dose expansion phase will enroll participants into 3 cohorts detailed as follows:

- **Part 2A (N=20):** PF-07260437 as monotherapy in participants with HR+ HER2- BrCa showing high B7-H4 expression, 2L+ who have progressed after at least 1 line of standard of care CDK4/6 inhibitor and 1 line of standard of care endocrine treatment. De novo paired pre- and on-treatment biopsies are mandatory for 5 participants.
- **Part 2B (N=20):** PF-07260437 as monotherapy in participants with HR+ HER2- BrCa, 2L+ who have progressed after at least 1 line of standard of care CDK4/6 inhibitor and 1 line of standard of care endocrine treatment, or 2L+ TNBC who have progressed after at least 1 line of SOC systemic therapy (eg 1L chemotherapy in combination with an immune checkpoint inhibitor if PD-L1+ or chemotherapy alone if PD-L1 negative/low). Approximately 10 HR+ HER2- BrCa and approximately 10 TNBC participants should be enrolled. De novo paired pre- and on-treatment biopsies are mandatory for approximately 5 HR+ HER2- BrCa participants and 5 TNBC participants. No biomarker selection based on B7-H4 expression.
- **Part 2C (N=20):** PF-07260437 as monotherapy in participants with TNBC showing high B7-H4 expression, 2L+ who have progressed after at least 1 line of SOC systemic therapy (eg, 1L chemotherapy in combination with an immune checkpoint inhibitor if PD-L1 positive or chemotherapy alone if PD-L1 negative/low). De novo paired pre- and on-treatment biopsies will be mandatory for 5 participants.

Depending on the results of preclinical combination in vivo efficacy data, emerging clinical monotherapy safety and efficacy, PF-07260437 combination cohorts may be added, including combination with CDK4/6 inhibitor and/or endocrine therapies in HR+ HER2- BrCa and combination with checkpoint inhibitors in TNBC.

All participants will undergo up to 28 days of screening prior to first dose. Eligible participants will then receive study intervention for up to 2 years, or until disease progression defined by irRECIST, unacceptable toxicities, a decision by the participant (withdrawal of consent or no longer willing to participate) or investigator to discontinue treatment, or study termination. Note: If a participant is classified as having PD during an on-treatment tumor assessment, then confirmation of PD by a second scan in the absence of rapid clinical deterioration is required per irRECIST.

### Number of Participants

Total number of participants for Part 1 and Part 2 combined, is estimated to be approximately 100.

Approximately 35 participants are expected to be enrolled into 1 of 5-7 sequential dose levels in Part 1 including at least 6 participants treated at the MTD. The actual number of participants enrolled will depend on the tolerability of PF-07260437 and the number of dose levels that are required to determine MTD/RDE.

Approximately 60 participants are expected to be enrolled into 3 cohorts in Part 2: Part 2A, Part 2B and Part 2C, with approximately n=20 participants in each cohort. Twenty participants for each cohort is clinically sufficient to evaluate safety signals.

### **Intervention Groups and Duration**

The total duration of the study from the beginning of screening to the safety follow-up visit is approximately 2 years.

### **Safety Review Committee**

This study will use an SRC. The SRC will be comprised of participating investigators or their medically qualified designee(s) who have at least 1 participant enrolled in the study and the Pfizer medical monitor or designee. The SRC members will have voting rights for dose escalation decisions.

### **Statistical Methods**

There is no formal hypothesis testing in this study.

Unless otherwise specified, summaries will be presented by dose group and overall. Descriptive statistics, such as the mean, standard deviation, coefficient of variation, median, minimum, and maximum values, will be provided for continuous endpoints. The rates of binary endpoints will be provided along with the corresponding 2-sided 95% CIs using an exact method. Time-to-event endpoints will be summarized using the Kaplan-Meier method and displayed graphically when appropriate. Median event times and 2-sided 95% CIs for each time-to-event endpoint will be provided.

The dose escalation in Part 1 of the study will be guided by a Bayesian analysis of DLT data for PF-07260437. Dose toxicity is modelled using 2-parameter logistic regression for the probability of a participant experiencing a DLT at the given dose.

After each cohort of participants, the posterior distribution for the risk of DLT for new participants at different doses of interest for PF-07260437 will be evaluated separately for cohorts with and without priming, taking into account the different DLT observation periods (28 days for the regimen without priming; priming doses plus 2 full doses for the regimen with priming). The posterior distributions will be summarized to provide the posterior probability that the risk of DLT lies within the following intervals:

Under-dosing:	[0, 0.16]
Targeted dosing:	[0.16, 0.33]
Overdosing:	[0.33, 1]

Dosing decisions are guided by the EWOC principal (Rogatko et al, 2007). A dose may only be used for newly enrolled participants if the risk of overdosing at that dose is less than 25%.

Recommendation from the BLRM, along with safety (AEs, SAEs), laboratory, PK, biomarker, and other relevant data, will be used at the time of each dose escalation and for MTD/RDE determination.

A weakly informative prior was used as there were no relevant human historical DLT data available.. For details, please see C4431001 Technical Supplement to Appendix 10.9.

[figure not shown]
For Part 2, the expansion arms will be conducted to assess efficacy as well as safety and tolerability of PF-07260437.

In Part 2, the secondary endpoint of overall response by RECIST version 1.1 and by irRECIST will be summarized and listed by expansion cohort and disease type. The secondary endpoints of DOR (RECIST version 1.1, irRECIST) , PFS (RECIST version 1.1, irRECIST), TTP (RECIST version 1.1, irRECIST), and OS will be summarized (graphically where appropriate) and listed by expansion cohort and disease type.

AEs will be graded by the investigator according to the NCI CTCAE version 5.0 and coded using the MedDRA. The number and percentage of participants who experienced any AE, SAE, treatment-related AE, and treatment-related SAE will be summarized according to worst toxicity grades. The summaries will present AEs on the entire study period.

### **2.3. Schema**

A diagram of the study design is displayed in [Figure 1](#).

**Figure 1. Study Schema**

\* A priming dose escalation may be initiated if criteria is met.

### 3. ENDPOINTS AND BASELINE VARIABLES: DEFINITIONS AND CONVENTIONS

#### 3.1 PRIMARY ENDPOINT(S)

##### Part 1

Determination of MTD will be performed using Per-protocol analysis set (evaluable for MTD). The dose escalation in Part 1 of the study will be guided by a Bayesian analysis of DLT data for PF-07260437. Dose toxicity is modelled using 2-parameter logistic regression for the probability of a participant experiencing a DLT at the given dose for the monotherapy and using BLRM model specifically developed for combinations separately for regimens with and without priming. A weakly informative prior distribution based on nonclinical/expert opinion information will be used to define the prior distribution for the PF-07260437 monotherapy dose escalation.

Dosing decisions are guided by the EWOC principal ([Rogatko et al, 2007](#)). A dose may only be used for newly enrolled participants if the risk of overdosing at that dose is less than 25%.

Recommendation from the BLRM, along with safety (AEs, SAEs), laboratory, PK, biomarker, and other relevant data, will be used at the time of each dose escalation and for MTD/RDE determination.

##### **Prior distributions:**

Weakly informative prior distributions based on pre-clinical/expert opinion information will be chosen for the logistic parameters for prior distribution in Part 1.

A MAP approach will be used to derive the prior distribution for model parameters used in Part 1 with priming based on the data collected in Part 1 without priming. The MAP prior for the logistic model parameters for this study is the conditional distribution of the parameters given the historical data ([Neuenschwander et al, 2010](#); [Schmidli et al, 2014](#)). MAP priors are derived from hierarchical models, which take into account possible differences between the studies.

##### **Starting dose:**

The starting dose for the monotherapy PF-07260437 is SC injection 100 µg Q2W. This dose satisfies the EWOC criterion.

##### **Stopping criteria:**

The sponsor estimates that the maximum number of participants in the Part 1 dose escalation portion of the trial is 40 participants. However, the actual number may be more or less based on observed PK and safety. The dose escalation will stop when the following criteria are met:

- At least 6 participants have been treated at the recommended MTD or RDE.
- The dose  $d$  for PF-07260437 satisfies 1 of the following conditions for the monotherapy part:

- The probability of target toxicity at dose d exceeds 50%, ie,  $\Pr(0.16 \leq d < 0.33) \geq 50\%$ , or
- A minimum of 15 participants have been treated in Part 1.

### Part 1 and Part 2

Incidence of AEs estimated in the safety analysis population during the AE-evaluation period, defined as the time from the first dose to earliest of 28 days post last dosing date and day of new anti-cancer therapy-1 day.

- **Variable:** Occurrence of AEs. AEs are defined in Section 8.3.
- **Analysis population:** Safety analysis set defined as participants who receive at least 1 dose of study treatment without regard to tolerability or duration of treatment.
- **Population-level summary measure:** Incidence of AEs defined as the number of participants with AEs in the AE-evaluation period divided by the number of participants in the analysis population. AEs will be summarized by type, frequency, severity (as graded by NCI CTCAE version 5), timing, seriousness, and relationship to treatment.

### 3.2 Secondary Endpoint(s)

#### Part 1 and Part 2

##### irAEs

irAEs as characterized by type, frequency, severity (as graded by NCI CTCAE v5) timing, seriousness, and relationship to study therapy.

#### Single-Dose and Steady-State PF-07260437 Pharmacokinetic Analysis

Serum concentrations of PF-07260437 will be summarized descriptively (n, mean, standard deviation, coefficient of variation, median, minimum, maximum, geometric mean, and its associated coefficient of variation) by dose, cycle, day, and nominal time.

Individual participant serum concentration-time data within a dose interval after Cycle 1 Day 1 and Cycle 2 Day 1 will be analyzed using noncompartmental methods to determine single and multiple dose PK parameters.

Single dose PK parameters to be estimated will include the serum  $C_{\max}$ ,  $T_{\max}$  and  $AUC_{\text{last}}$ , and as data permit,  $AUC$  from time 0 extrapolated to infinity ( $AUC_{\text{inf}}$ ),  $t_{1/2}$ , clearance ( $CL/F$  for SC dosing and  $CL$  for IV dosing) and volume ( $V_z/F$  for SC dosing and  $V_{ss}$  for IV dosing).

Multiple dose PK parameters to be estimated will include  $C_{\max,ss}$ ,  $T_{\max,ss}$ ,  $AUC_{ss,\tau}$ ,  $C_{\min,ss}$ , clearance ( $CL_{ss}/F$  for SC and  $CL_{ss}$  for IV) and as data permit, volume ( $V_z/F$  for SC or  $V_{ss}$  for IV),  $t_{1/2}$ , and  $R_{ac}$  ( $AUC_{ss,\tau}/AUC_{sd,\tau}$ ). The single dose and steady-state PK parameters will be summarized descriptively (n, mean, standard deviation, coefficient of variation, median, minimum, maximum, geometric mean, and its associated coefficient of variation) by dose level and cycle.

Dose normalized  $AUC_{\text{inf}}$  ( $AUC_{\tau}$  at steady state) and  $C_{\text{max}}$  will be plotted against dose (using a logarithmic scale) by cycle. These plots will include individual participant values and the geometric means for each dose.

### **Analysis of Immunogenicity Data**

For the immunogenicity data, the percentage of participants with positive ADA and neutralizing antibodies each will be summarized. For participants with positive ADA or neutralizing antibodies, the magnitude (titer), time of onset, and duration of ADA or neutralizing antibodies response will also be described, if data permit.

### **Part 2**

#### **Efficacy Analysis**

Response Evaluable Set will be used for all response-related analyses including ORR, DoR, PFS, and TTP (RECIST, irRECIST). Tumor response will be presented in the form of participant data listings that include, but are not limited to tumor type, tumor response at each visit, and best overall response. OS will be reported on the Full Analysis Set as well as on the mITT.

Data will be summarized (also graphically where appropriate) and listed by expansion cohort.

### **3.3 Tertiary/Exploratory Endpoint(s)**

#### **Part 1**

#### **Efficacy Analysis**

Response Evaluable Set will be used for ORR and PFS (RECIST, irRECIST). Tumor response will be presented in the form of participant data listings that include, but are not limited to tumor type, tumor response at each visit, and best overall response.

Data will be summarized (also graphically where appropriate) and listed by dose level.

#### **Part 1 and 2**

#### **Analysis of Pharmacodynamics**

Results of exploratory endpoint analyses will be described in the CSR to the extent possible. Due to the exploratory nature of the endpoints, the associated data analyses may not be complete at the time of CSR preparation. If results of exploratory endpoint analyses cannot be included in the CSR, they will be disseminated to the scientific community to the extent possible through presentation at scientific meetings and/or publication in peer-reviewed scientific journals.

### 3.4 Baseline Variables

Baseline characteristics will be collected according to [Schedule of Activities](#) as specified in the protocol. For the primary analyses, no baseline variable will be used for stratification or as covariates in the statistical analysis. Unless otherwise specified, the baseline value is defined as the value collected at the time closest to, but prior to, starting the study intervention administration in the first cycle.

Laboratory baseline will be the last predose measurement taken before the first dose of any component of the study intervention.

### 3.5 Safety Endpoints

The on-treatment period will be used for all safety assessments. The on-treatment period is defined as the period that starts with the first dose of study treatment and ends at minimum (last dose of study treatment + 30 days, start of new anti-cancer therapy - 1 day).

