8.3.1. Time Period and Frequency for Collecting AE and SAE Information

The time period for actively eliciting and collecting AEs and SAEs (“active collection period”) for each participant begins from the time the participant provides informed consent, which is obtained before the participant’s participation in the study (ie, before undergoing any study-related procedure and/or receiving study intervention), through and including a minimum of 28 calendar days, except as indicated below, after the last administration of the study intervention.

Follow-up by the investigator continues throughout and after the active collection period and until the AE or SAE or its sequelae resolve or stabilize at a level acceptable to the investigator.

For participants who are screen failures, the active collection period ends when screen failure status is determined.

If the participant withdraws from the study and also withdraws consent for the collection of future information, the active collection period ends when consent is withdrawn.

If a participant permanently discontinues or temporarily discontinues study intervention because of an AE or SAE, the AE or SAE must be recorded on the CRF and the SAE reported using the CT SAE Report Form.

Investigators are not obligated to actively seek information on AEs or SAEs after the participant has concluded study participation. However, if the investigator learns of any SAE, including a death, at any time after a participant has completed the study, and he/she considers the event to be reasonably related to the study intervention, the investigator must promptly report the SAE to Pfizer using the CT SAE Report Form.

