#### 6.1.2 Adverse Events (Part 1 and Part 2)

- Analysis set: Safety analysis set.
- Analysis methodology:

AEs will be characterized by type, frequency, severity (as graded by NCI CTCAE version 5.0, except CRS, which will be graded by ASTCT criteria (Lee et al., 2019)) timing, seriousness, and relationship to study therapy. Further description is given in Section 0. The primary focus will be on TEAEs. TEAEs is defined as any AE that occurs during the on-treatment period. AEs that occur after the on-treatment period may still be recorded in the clinical database and will be included in the AE listings, but will not be included in the on-treatment emergent AE summaries.

See Section 0 for details on the specific AE summaries to be provided.

- Missing data: If an AE start or stop date is missing, imputation will be performed. The imputed dates will be used to determine whether the AE is to be included in the TEAE summary. The missing AE start or stop dates will be listed as is in AE listings. When the CTCAE grade is missing for an AE, the AE will be excluded from the CTCAE grade summary table.

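### The primary adverse event estimand closes 28 days after the last dose, but the SAP's primary summaries count events over a 30-day on-treatment period

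*SAP*

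**What the plan says.** **The estimand.** SAP 2.1.1 defines the AE-evaluation period as "the time from the first dose to earliest of 28 days post last dosing date", with the day before new anti-cancer therapy as the alternative end. SAP 3.1 and protocol 9.1.1.1 and 9.3.2 give the same rule, so 28 days is stated four times.

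**The analysis.** SAP 3.5 ends the on-treatment period at the minimum of two dates: "last dose of study treatment + 30 days" and the day before new anti-cancer therapy. It fixes the scope in one sentence: "The on-treatment period will be used for all safety assessments". SAP 6.1.2, the analysis section for the primary AE endpoint, says "The primary focus will be on TEAEs" and then "TEAEs is defined as any AE that occurs during the on-treatment period". Later events go into listings but not into the treatment-emergent summaries. SAP 6.1.3 (laboratory abnormalities, also a primary endpoint) and SAP 6.2.1 (irAEs, secondary) rely on the same on-treatment period.

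**Collection.** Protocol 8.3.1 runs active collection through "a minimum of 28 calendar days, except as indicated below, after the last administration" of study intervention. Protocol 7.1 places the safety follow-up visit 28 to 35 days after discontinuation.

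**Other wording.** SAP 3.5.1 and 6.6.1 describe AE summaries over the entire study period. SAP 6.6.1 also splits deaths into on and off treatment at 30 days.

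**The concern.** An estimand fixes which events count, and the analysis should count the same ones. Here two readers of the SAP can each follow it faithfully and produce different primary tables. One who starts from sections 2.1.1 and 3.1 stops at day 28. One who starts from sections 3.5 and 6.1.2 stops at day 30. Nothing says which governs, and nothing labels either as supplementary. The entire-study-period wording adds a third description of the AE reporting window.

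The trial has no hypothesis test. The AE incidences are therefore themselves the primary safety result for both parts, and their window should be beyond doubt. The longer window also reaches past the period in which the protocol guarantees that participants are actively asked about events.

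**Working it through.** No sample size, power or error rate is involved. The check sets the two definitions side by side and works out when they give different answers.

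**Inputs**
- Estimand window: protocol 9.1.1.1 and 9.3.2; SAP 2.1.1 and 3.1.
- Analysis window: SAP 3.5, used in SAP 6.1.2.
- Measure: participants with AEs divided by participants in the safety analysis set (SAP 2.1.1).
- Denominators: about 20 per Part 2 cohort and about 3 per Part 1 dose level (SAP 2.2).

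**Step 1: length of the gap.** Count days from the last dose, and let new therapy start on day k.
- Estimand end = min(28, k − 1)
- Analysis end = min(30, k − 1)

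| New therapy | Estimand ends | Analysis ends | Gap |
|---|---|---|---|
| Day 29 or earlier | day k − 1 | day k − 1 | 0 days |
| Day 30 | day 28 | day 29 | 1 day |
| Day 31 or later, or none | day 28 | day 30 | 2 days |

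The largest gap is 30 − 28 = 2 days. It vanishes for anyone who starts new therapy by day 29.

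**Step 2: who changes a rate.** The numerator counts participants, not events. A participant with onset on day 29 or 30 moves from not counted to counted only if nothing earlier already placed them in that row. In a worst-grade table, the late event must raise the grade. In either case new therapy must not already have closed both windows.

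**Step 3: size per participant.**
- Part 2 cohort: 1/20 = 5 percentage points.
- Part 1 dose level: 1/3 ≈ 33 percentage points.

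**Step 4: how many such participants.** The documents give no event rates by day after the last dose and no rate of starting new therapy, so this number cannot be derived.

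**Step 5: coverage of days 29 and 30.** The collection minimum ends at day 28. The follow-up visit may fall on day 28 or as late as day 35, counted from discontinuation. A participant seen early may not be asked about days 29 and 30; one seen later would be. Coverage is therefore not guaranteed and may differ between participants.

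**The case against.** The strongest reply is that two days in a descriptive tabulation hardly matter. The any-AE row is likely to be almost unaffected, because most participants who contribute to it will have had an event well before day 29. Events after the on-treatment period are still listed, so no data are lost. All of this is fair, and it limits the importance of the point. It does not remove the conflict, since neither document reconciles the windows.

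It can also be said that 28 days is a floor for collection. Follow-up is timed from discontinuation, which may come some days after the last dose, so many visits will reach day 30. That stands. It shows that coverage is often likely, not that it is guaranteed.

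Protocol section 9 lets the SAP modify the planned methods. But the SAP does not present 30 days as a change and restates 28 days twice. Major changes to the primary endpoint definitions or analyses must also appear in a protocol amendment; whether two days is major is a matter of judgement.

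A reader might infer three stronger things that the documents do not support:
- **That every event on day 29 or 30 shifts an incidence by 5 points.** The measure counts participants, so most late events would change nothing.
- **That ascertainment on those days is tilted towards serious events.** For treated participants during collection, the protocol separates serious from nonserious recording once new anti-cancer therapy starts (8.3.1.2), and both windows have closed by then. The restriction to related SAEs in 8.3.1 applies after study participation ends. Uneven coverage follows from the text; a tilt in a known direction does not.
- **That the on/off-treatment death table also has two definitions.** SAP 6.6.1 gives only the 30-day one, and neither document has a 28-day version of that table.

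**Conclusion.** The point holds as an inconsistency in the SAP: the primary AE estimand uses 28 days and its analysis section uses 30. The gap is at most 2 days. The expected numerical effect is small, although one affected participant is worth 5 percentage points in a cohort of 20 and about 33 in a dose level of 3. Those figures assume the planned group sizes and a participant who meets the conditions in step 2 of the working. The number of such participants is unknown.

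A reader might carry this over to dose escalation, which would be wrong. Dose-limiting toxicities have their own observation period, 28 days without priming and longer with it, so determination of the maximum tolerated dose is not touched. The conflict deserves correction because it sits in a primary endpoint and the remedy is cheap, not because it is likely to change a safety conclusion.

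**What to change.** 1. In SAP 3.5, change 30 days to 28 days. The AE, laboratory and irAE summaries in SAP 6.1.2, 6.1.3 and 6.2.1 then follow the estimand's window and stay within the guaranteed collection period. The gap falls from 2 days to 0.
2. In SAP 3.5.1 and 6.6.1, state that, for the primary AE summaries, the entire study period means this window. Without that, a second description of the window would remain after the first change.
3. Optionally, align the 30-day death split in SAP 6.6.1. This is harmonisation only; the estimand does not require it.

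Items 1 and 2 cost SAP wording only and can be made before database release. Keeping 30 days throughout is possible but is not the cheap route. It would change the estimand in both documents and the minimum collection period in protocol 8.3.1, and so would need a protocol amendment.
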